**Figure 8. Mediation models that will be fit to the S4S sample, with brain data articulated as mediators.**

**Figure 7. Brain regions expected to be modulated by polygenic risk for alcohol-related aggression. Red = reward circuit, blue = prefrontal control circuit.**

#### Feasibility

I have performed numerous functional and structural MRI experiments using these laboratory aggression procedures and statistical techniques. [My lab has also completed a complex MRI study using this aggression paradigm, which recruited 112 participants over 1 year, suggesting that

*[the large MRI sample size in this proposal can be readily obtained at VCU.]* Prior research using this laboratory aggression paradigm has shown that aggression on this task is reliably increased by alcohol administration and can be safely and effectively administered in the MRI scanner. Therefore, this task is well-adapted for the MRI environment, and for alcohol administration.

Power analysis. FMRIPower v1.0^67 [and powerMediation] packages were used to analyze pilot fMRI data from previous research on differences between groups (that are at-risk for aggression) in aggression-related brain activity. Using the ventral striatum (a core node of the brain's reward circuit) as the region-of-interest, [mediation modeling will have at least 80% power to detect a small indirect effect (0.09%) between risk groups with 198 participants, 99 per group. Based on previous work with this aggression paradigm, 4 of these participants will likely be suspicious of our deception. As such, a sample size of 202 participants was selected (101 per group).]

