**Aim 4: Identify functional and structural brain mechanisms that transmit the genetic effects on alcohol-influenced aggression.** *Hypothesis 4:* Polygenic risk scores for alcohol-influenced aggression will be associated with greater laboratory aggression, through changes in brain structure and function.

This proposal capitalizes on the resources available through [NIH-funded publicly-available datasets from the database of Genotypes and Phenotypes (dbGaP)] and VCU's Spit for Science (S4S) project, on which my primary mentor, [name] is a Principal Investigator. Drs. [name] and [name] (Co-Mentors) also play substantial roles in many of these projects. I would begin by analyzing existing data from [the dbGaP discovery sample], then seeking to replicate these findings with ongoing data collection for Spit for Science at my current institution, VCU. Finally, I would conduct a new MRI brain imaging study, using S4S participants (recruited based on their underlying genetic risk profiles) analyses in order to leverage my existing skillset in neuroimaging and laboratory aggression measurement and further accomplish the proposed research aims.

Accomplishing these aims would advance my long-term goal to become an independent alcohol investigator who integrates across multiple disciplines to study the factors that influence alcohol-influenced aggression. These activities would set the stage for R01-level applications to investigate the environmental factors that influence these effects, and biologically-informed interventions that might ameliorate them.

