**Figure 3. Frequencies of a subset of COGA participants' alcohol-influenced aggression scores.**

heritability of  $h^2 = 0.2$ , a type I error rate of 0.05, and a variance of SNP-derived genetic relationships of .00002, suggested that 80% power for the proposed GCTA can be obtained with 4,430 participants. The [discovery] sample far exceeds this sample size at over [31,000] participants. GWAS power analyses, implemented via the GWAS.PC v1.0 package for R statistical software were also performed to determine the minimum effect size (in units of % variance explained) that [the discovery sample could detect with 80% power. Calculations were based on the planned detection of multiple, additive SNP markers, an alpha level of .05, and a minor allele frequency of 0.05, revealing that the proposed GWAS is able to detect effect sizes of 0.09% variance-explained and larger. However, this is likely an optimistic assessment as this power analysis did not account for the moderating effects of ethnicity/race and the genetic relatedness of participants (yet recent research has indicated that GWAS power is not significantly affected by underlying genetic relationships between participants).]

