#### Feasibility

This first phase of Aim II builds upon the already successful and ongoing S4S project, by simply adding a short online survey to the existing S4S battery of questionnaires. However, undergraduates at VCU differ from the [diverse members of the discovery sample] in ways that may suppress the amount of alcohol-influenced aggression among the S4S sample (e.g., lower levels of alcohol misuse and dependence). A pilot sample of VCU undergraduates were asked about their aggressive behavior and whether it occurred in the context of

alcohol misuse or not. Of the 166 female and male participants surveyed, 53.6% indicated that they had participated in a physical fight in the past 5 years (30.1% had been in more than 1 fight). Of those who had previously fought, 38.2% participated in this fight under the influence of alcohol. These initial estimates suggest that 1 out of 5 VCU undergraduates (i.e., 20.48%) have perpetrated a substantial act of physical aggression under the context of alcohol misuse. This prevalence rate indicates that the much larger pool of potential S4S participants is likely to exhibit alcohol-influenced aggression at a sufficient rate to test associations with polygenic risk scores.

Power analysis. The expected S4S sample size of 10,000 students will provide 80% power to detect a genome-wide effect of 0.35% variance explained in alcohol-influenced aggression, or larger. [The S4S GWAS is likely to be under-powered, yet performing this replication GWAS will serve as a valuable training in how to collect genomic data and use it to replicate previous GWAS results.]

Potential Problems and Alternative Strategies. The S4S sample GWAS may not replicate the profile of SNPs found in the [discovery] sample, as the S4S sample is smaller and is comprised of undergraduate students. However, replication is a crucial step in genomic science and this is as important training experience.

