#### Analytic Plan

A [mixed]-effects general linear model (GLM) will test

[figure not shown]
the test the prediction that the high polygenic risk group will select louder noise blasts after alcohol

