**Figure 6. Anticipated results comparing polygenic risk groups on their aggressive behavior, after alcohol or placebo.**

[figure not shown]

the task. Multiple comparisons corrections will be conducted using nonparametric threshold-free cluster enhancement. Mediation models will then be fit in which the effect of polygenic risk score group on aggression (after the alcohol administration) will be mediated by functional and structural brain estimates from brain regions that were significantly different between the two polygenic risk groups (Figure 8). The PROCESS macro for SPSS will be used to conduct nonparametric bootstrapping (using 5,000 bootstrapped resamples) to test the significance of each neural mechanism's indirect effect.

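### Does the imaging power statement (80% for an indirect effect of 0.09%, 198 participants) undermine the sample size of 202?

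*Combined protocol and SAP*

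**What the plan says.** In the combined protocol and SAP, Phase II, Feasibility, the power paragraph names two software packages and says they were applied to "pilot fMRI data from previous research on differences between groups (that are at-risk for aggression) in aggression-related brain activity", with the ventral striatum as the region of interest. It then states "mediation modeling will have at least 80% power to detect a small indirect effect (0.09%) between risk groups with 198 participants", split 99 per group. Four participants are expected to see through the deception, so 202 are recruited, 101 per group.

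Three other places bear on how to read that sentence:

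- **The hypothesis.** Hypothesis 4 in the Specific Aims reads "Polygenic risk scores for alcohol-influenced aggression will be associated with greater laboratory aggression, through changes in brain structure and function". The indirect effect is therefore part of what is claimed.
- **The tests.** The Phase II Analytic Plan has a mixed-effects model for the "prediction that the high polygenic risk group will select louder noise blasts after alcohol", and separate mediation models that use "nonparametric bootstrapping (using 5,000 bootstrapped resamples) to test the significance" of each indirect effect.
- **Other percentages.** The power paragraph for the discovery sample ends "revealing that the proposed GWAS is able to detect effect sizes of 0.09% variance-explained and larger". The one for the student replication sample gives "80% power to detect a genome-wide effect of 0.35% variance explained in alcohol-influenced aggression". Both name the scale; the imaging sentence does not.

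**The concern.** A power statement for mediation needs two paths: risk group to brain (a) and brain to aggression (b). It also needs the SDs, a significance level and the test. None of these is printed for the imaging study. The only percentages whose scale is stated are variance explained, and the discovery calculation has the same figure of 0.09%. Carried over to 198 people, an effect of that size would be almost undetectable.

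A second worry is that 99 per group is what an ordinary two-group comparison needs for a difference of 0.40 SD. If the figure came from such a calculation, the 80% would describe path a only and not the bootstrapped indirect effect that tests the mediation part of Hypothesis 4. A reader of a null mediation result could then be misled about what the study was able to detect.

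**Working it through.** **Inputs from the document.** N = 198, 99 per group; four exclusions; effect 0.09%; power at least 80%; planned test a bootstrap with 5,000 resamples.

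**Assumed, because not printed.** Two-sided alpha 0.05 (critical value 1.96) and no direct effect of group on aggression. The 0.05 in the discovery-sample power paragraph belongs to the genetic calculations.

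**The plan's own sum.** 198 + 4 = 202, or 101 per group. This is correct. The 80% itself cannot be reproduced, so the possible readings are tried in turn.

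**1. Variance explained, R² = 0.0009.** Noncentrality = √(198 × 0.0009 / 0.9991) = 0.422. Power ≈ Φ(0.422 − 1.96) + Φ(−0.422 − 1.96) = 0.062 + 0.009 = 7%. For 80%, N ≈ (1.960 + 0.842)² × 0.9991 / 0.0009 ≈ 8,700.

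**2. Product of standardised paths.** Take se(a) = √[(1 − a²)/N] and se(b) = √[(1 − b²)/(N(1 − a²))]. Joint-significance power is Φ(a/se(a) − 1.96) × Φ(b/se(b) − 1.96).

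| Reading | a, b | Joint power | Percentile bootstrap (simulated) |
|---|---|---|---|
| ab = 0.0009 | 0.03, 0.03 | 0.062 × 0.062 = 0.4% | 0.3% |
| (ab)² = 0.0009, so ab = 0.03 | 0.173, 0.173 | 0.697 × 0.683 = 48% | 44% |
| ab = 0.09 (percent sign dropped) | 0.30, 0.30 | 0.993 × 0.988 = 98% | 98% |
| ab = 0.09 (percent sign dropped) | 0.60, 0.15 | 1.000 × 0.400 = 40% | 40–41% |

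The last two rows have the same product and very different power. The product alone does not fix the answer, even on a standardised scale.

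**3. Group difference in signal change.** For d = 0.40, noncentrality = 0.40 × √(99/2) = 2.81 and power ≈ Φ(2.81 − 1.96) = 80.4% (80.0% by the t distribution). A difference of 0.09 gives d = 0.40 if the SD is 0.225, which is assumed. This matches 99 per group, but it tests path a alone. As a correlation, that path is 0.40/√(0.40² + 4) = 0.196. Simulated power for the indirect effect, percentile to bias-corrected bootstrap, is then 21–30% at b = 0.10, 61–72% at b = 0.20 and 79–84% at b = 0.30.

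**4. Indirect effect in raw units, sentence unchanged.** Group is coded 0/1, with residual SDs σM (brain) and σY (aggression). Then se(a) = σM√(4/N) and se(b) = σY/(σM√N).

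- Assume a = 0.09, b = 0.01, σM = 0.20, σY = 0.008. The product is 0.0009, which is 0.09%.
- se(a) = 0.20 × √(4/198) = 0.0284, ratio 3.17, power Φ(1.21) = 0.886.
- se(b) = 0.008/(0.20 × √198) = 0.00284, ratio 3.52, power Φ(1.56) = 0.940.
- Joint power = 0.886 × 0.940 = 83% (82% by simulation). The Sobel test gives 67% by simulation.
- With b = 1 and σY = 0.80 the product is 0.09, and both ratios, hence the power, are the same.

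At fixed N, raw-unit power depends only on a/σM (here 0.45) and bσM/σY (here 0.25). Rescaling the outcome changes the printed product without changing the power. The number 0.09% therefore says nothing about power until the SDs are known.

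**The case for a change.** The strongest case for acting is that this sentence is the only stated basis for 202 and cannot be checked. The genetic power paragraph for the discovery sample does report its inputs (heritability, error rate, relationship variance, allele frequency), so the omission is not simply house style. The exact match of 99 per group to d = 0.40 makes it plausible that a group-comparison figure was labelled as mediation power. The raw-unit example works only because its SDs were chosen to make it work. Restating the sentence would cost little.

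Much of this stands. The 80% is unverifiable from the document, and the match to d = 0.40 is suggestive. But the match is not proof, and the raw-unit example needs to show only that the printed number and label can coexist with 80%, which it does. The inputs may also lie in the pilot data, the software runs or the reference attached to the sample size, none of which is available here. The Phase II Analytic Plan has lost text around its figures in extraction, so a significance level for Phase II cannot confidently be called absent. Finally, any restated sentence would have to be filled with the author's own numbers. Nothing in the document says what they are, or whether the detectable effect would turn out larger or smaller than intended.

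**Conclusion.** The concern does not call for a change. What is established is narrow: the imaging power figure cannot be reproduced, because the scale of the percentage, both paths, the SDs, alpha and the test used for power are not stated. With two-sided alpha 0.05, 99 per group and no direct effect, the readings above run from under 1% to 98%, and at least one reaches about 82% with the sentence as printed. That range reflects the assumptions put in. It is not evidence that 80% is false or that 202 is too small.

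The gap is one of reporting detail in a grant-style research plan. The recruitment target, the groups, the two-session design and the bootstrap test are all specified without reference to the missing inputs and would stay the same once these were supplied. When the mediation results are read, the bootstrap interval for each indirect effect will show what the data can and cannot exclude. A sensible analyst would rely on that interval and would not use the 80% to interpret a null finding.

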#### Potential Problems and Alternative Strategies

Participants in the low and high polygenic risk groups will likely differ on other variables (e.g., physical health) that might serve as problematic confounds. To address this, participants from each group will be closely-matched on age, sex, race, and socioeconomic status. The groups will be equated in physical and mental health as the screening procedures exclude any individuals with diagnosed physical or mental pathologies. There are also risks posed by the MRI environment, alcohol administration, and aggression task procedures. I have extensive MRI experience, participants undergo extensive screening procedures, and participants are under constant supervision by CARI center staff who are certified in safe MRI and alcohol administration procedures. CARI center staff are prepared to effectively handle any potential medical emergencies. If a brain abnormality is observed, a licensed radiologist is available through the CARI facility for consultation. The success of this study hinges on effective participant recruitment. Multiple offshoot studies using S4S data have been successful (e.g., an F31-funded fMRI study in [name] lab that recruits S4S participants for based on polygenic risk scores for externalizing behaviors). Further, the recruitment pool is large enough to provide many potential participants who meet this study's inclusionary criteria.

#### Benchmarks for Success

Table 3 summarizes the timeline of the major tasks for both Aim I and Aim II projects. These milestones provide benchmarks for success. [All manuscript submissions will target flagship journals of behavioral genetics and alcohol misuse (e.g., *Addiction Biology*, *Nature Genetics*).]

#### Summary and Future Directions

The proposed research integrates across disciplines, methodological and statistical approaches to investigate a costly and complex phenomenon: alcohol-influenced aggression. The studies will estimate the extent to which alcohol-influenced aggression is genetically heritable, and whether this heritability is distinct from general forms of aggressiveness and alcohol misuse. These studies

will also identify specific genome-wide polymorphisms that are linked to alcohol-influenced aggression and will seek to replicate these findings in an independent sample. Further, I will build upon these discoveries by combining neuroimaging with a laboratory alcohol administration to identify the neural pathways through which these genetic risk factors alter brain structure and functional responses to aggression after alcohol administration. These research and training activities are a logical extension from my current skillset and will enable him to pursue a career as an independent alcohol misuse researcher. I will use the skillset gained from the proposed projects to apply for an R01 to conduct a larger investigation of the environmental factors (e.g., childhood trauma) that interact with the genetic risk factors for alcohol-influenced aggression. The ultimate goal of such investigation is to construct and validate effective interventions that reduce violent behavior in the context of alcohol misuse. The novel training and research experiences that I will gain under this K01 award will provide the foundation for these future career steps.

**Table 3. Research activities by award year (Y).**

Activity	Y1	Y2	Y3	Y4	Y5
[Discovery] data preparation	X				
[Discovery] data analysis	X	X			
[Discovery manuscript submission]			[X]		
S4S genotyping data collection	X	X			
S4S genotyping data analysis			X		
[S4S genotyping manuscript submission]			[X]		
S4S neuroimaging data collection			[X]	X	
S4S neuroimaging data analysis					X
[S4S neuroimaging manuscript submission]					[X]
R01 application preparation				X	X
[R01 application submission]					[X]

## **TRAINING IN THE RESPONSIBLE CONDUCT OF RESEARCH**

Across the proposed award timeline, I will receive substantial training in the responsible and ethical conduct of research on human participants. Virginia Commonwealth University's (VCU) Office of Research and Innovation offers regular education and training activities in responsible conduct of research. In year 1, I will enroll in two VCU courses: CCTR 520: Fundamentals of Research Regulation (2 lecture hours, 2 credits) and OVPR 601: Scientific Integrity (1 lecture hour, 1 credit). In year 2, I will enroll in two VCU courses: OVPR 602: Responsible Scientific Conduct (1 lecture hour, 1 credit) and OVPR 603: Responsible Conduct of Research (1 lecture hour, 1 credit). In addition, regular workshops are offered by various VCU departments, centers, and institutes in areas such as the informed consent process, adverse and reportable events in research, vulnerable populations, bio-safety, data management, and conflicts of interest. I will attend these regular workshops and will also gain informal research ethics training in interactions with my primary and co-mentors. Further, my weekly laboratory meetings with doctoral students and undergraduate research assistants will regularly involve discussions of the responsible conduct of research. As a VCU researcher, I have completed the Basic, Social/Behavioral, and Biomedical courses in responsible conduct of research from the Collaborative Institution Training Initiative (CITI). I will keep these certifications up-to-date via biennial online courses.
